12.2.1 Quality of Life – Bronchiectasis (QOL-B)

The first secondary efficacy endpoint is the change from baseline in the QOL-B domain scores at the Days 28, 56, and 84 visit, and Day 84/EOT. Descriptive statistics will be provided for each domain at each time point and ANCOVA estimates will be provided as described in [Section 12.2](#). A graph of the cumulative distribution of the change from baseline to Day 84 for the respiratory domain by treatment group will also be provided.

12.2.2 St George's Respiratory Questionnaire (SGRQ)

The second secondary efficacy endpoint is the change from baseline in the SGRQ global and component scores at the Day 28, 56, and 84 visit, and Day 84/EOT. Descriptive statistics will be provided for the global score and each component score at each time point and ANCOVA estimates will be provided as described in [Section 12.2](#).

12.2.3 Patient-reported Outcomes Measurement Information System (PROMIS)

The third secondary efficacy endpoint is the change from baseline in the PROMIS Fatigue 7a Short Form standardized score at the Day 28, 56, and 84 visit, and Day 84/EOT. Descriptive statistics will be provided for the standardized score at each time point and ANCOVA estimates will be provided as described in [Section 12.2](#).

12.2.4 Patient Global Impression-Change (PGI-C)

The fourth secondary efficacy endpoint is the PGI-C assessed at the Day 28, 56, and 84 visit, and Day 84/EOT.

Subject response will also be categorized as subjects who experienced an improvement and those who did not experience improvement. The number and percentage of subjects in each category (improvement/no improvement) will be presented by treatment group along with exact 2-sided 95% CIs using the Clopper-Pearson method. The difference between treatment groups in percentages of subjects experiencing improvement will be presented along with a 2-sided 95% exact CI. The p-value from a Fisher's exact test will be provided.

12.2.5 Patient Global Impression-Severity (PGI-S)

The fifth secondary efficacy endpoint is the PGI-S response at the Day 28, 56, and 84 visit, and Day 84/EOT. The PGI-S will be analyzed similarly to the PGI-C as described in [Section 12.2.4](#) except subject response will be grouped as subjects with responses of Not Present/Mild versus those with responses of Moderate/Severe. The difference between treatment groups in percentage of subjects with a response of Not Present/Mild will be presented along with a 2-sided 95% exact CI. The p-value from a Fisher's exact test will be provided.

An additional analysis of the PGI-S will summarize change from baseline as improved, no change and worsened at the Day 28, 56 and 84 visit, and Day 84/EOT. The number and percentage of subjects in each change category will be provided.

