8.13.4 Patient Clinical Impression of Severity

The PGI-S is a self-administered, single question assessed using a 7-point scale that measures a subject's perception of disease severity.

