12.5.2 Secondary Efficacy Endpoints

12.5.2.1 Patient-Reported Outcomes and Quality of Life

For each patient-reported outcome and quality of life endpoint, analyses will be conducted in the ITT Analysis Set. Available data will be used; there will be no substitutions for missing data.

The QOL-B includes domains for physical functioning, role functioning, vitality, emotional functioning, social functioning, treatment burden, health perceptions and respiratory symptoms. For each domain, scores will be standardized on a 0 to 100 scale. Descriptive statistics for each domain at baseline and each visit will be presented by treatment group. The change from baseline to each visit will be analyzed using an analysis of covariance (ANCOVA) and the least squares (LS) mean, standard error (SE) of the LS mean and 2-sided 95% CI for the LS mean will be provided for each treatment group. The difference in LS means between treatment groups, 2-sided 95% CI and p-value will also be provided.

For the SGRQ, the global score and score for each component (symptoms, activity, and impacts) will be determined. Descriptive statistics for the global score and each component score at each visit will be presented by treatment group. The change from baseline to each visit will be analyzed using an ANCOVA, and the LS mean, and 2-sided 95% CI for the LS mean will be provided for each treatment group. The difference in LS means between treatment groups, 2-sided 95% CI and p-value will also be provided.

For the PROMIS Fatigue 7a Short Form, raw scores are converted to a standardized score. Descriptive statistics for the standardized score at baseline and each visit will be presented by treatment group. The change from baseline to each visit will be analyzed using an ANCOVA, and the LS mean, SE of the LS mean, and 95% CI for the LS mean will be provided for each treatment group. The difference in LS means between treatment groups, 95% CI and p-value will also be provided.

For the PGI-S, the number and percentage of subjects with each response will be presented by visit and treatment group. The PGI-S will also be categorized as mild/not present vs. moderate/severe and the number and percentage of subjects in each category will be presented by visit and treatment group. Exact 2-sided 95% CIs using the Clopper-Pearson method for the percent improved and a p-value from Fisher's exact test will be provided.

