Appendix 1 Schedule of Assessments

Study Phase	Screening	Double-Blind Treatment					Follow-up
		Day 1 Baseline ^b	Day 14 Tele-visit ^c	Day 28	Day 56	Day 84/EOT	
Visit Name	Screening ^a						30 Day Safety Follow-up Call ^d
Visit Window	N/A	N/A	± 2d	± 3d	± 3d	+5d /- 2d	+ 7d
Informed consent ^e	X						
Inclusion/exclusion criteria	X	X					
Medical history/current medical conditions	X						
Demography	X						
Physical examination	X					X	
Height	X						
Weight	X	X		X	X	X	
BMI	X						
Serum or urine pregnancy test ^f	X	X		X	X	X	
Vital signs (BP, HR, body temperature, and pulse oximetry) ^g	X	X		X	X	X	
Hematology ^h	X	X		X		X	
Serum chemistry	X	X		X		X	
Biomarkers (serum, plasma) ⁱ		X				X	
Sputum collection for microbiology ^j	X ^k	X		X	X	X	
CT scan of chest	X ^l					X	
12-lead ECG	X					X	
NTM Symptom Assessment Questionnaire	X	X		X	X	X	
St. George's Respiratory Questionnaire (SGRQ)		X		X	X	X	

Study Phase	Screening	Double-Blind Treatment					Follow-up
Visit Name	Screening ^a	Day 1 Baseline ^b	Day 14 Tele-visit ^c	Day 28	Day 56	Day 84/EOT	30 Day Safety Follow-up Call ^d
Visit Window	N/A	N/A	± 2d	± 3d	± 3d	+5d /- 2d	+ 7d
Quality of Life – Bronchiectasis (QOL-B)		X		X	X	X	
PROMIS-Fatigue Short Form 7a		X		X	X	X	
Patient Global Impression – Severity (PGI-S)		X		X	X	X	
Patient Global Impression – Change (PGI-C)				X	X	X	
Clinical Global Impression – Severity of Illness (CGI-S)		X		X	X	X	
Clinical Global Impression - Global Improvement Scale (CGI-I)				X	X	X	
Dispense test article		X		X	X		
Test article administration ^m		X	◀	▶	X		
Test article accountability and compliance				X	X	X	
Adverse events ⁿ	X	X	X	X	X	X	X
Prior/concomitant medications ^o	X	X	X	X	X	X	X

β-hCG = serum β-human chorionic gonadotropin; BMI = body mass index; BP = blood pressure; CT = computed tomography; d = day(s); ECG = electrocardiogram; eCRF = electronic case report form; EOT = end of treatment; HR = heart rate; ICF = informed consent form; MABc = *Mycobacterium abscessus* complex; MAC = *Mycobacterium avium* complex; N/A = not applicable; NTM = nontuberculous mycobacterial

- Screening period may occur for up to 8 weeks prior to randomization to allow for sputum microbiology results. Screening procedures may occur on separate days. Subjects may be randomized as soon as all screening procedures have been performed and results have been received to verify eligibility criteria.
- All Day 1/Baseline Visit procedures should be completed prior to subject dosing.

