11.3 Adjustments for Covariates

The model for the primary efficacy and some secondary efficacy analyses will include adjustments for randomization stratification factor:

- Prior treatment of NTM caused by MABC at baseline status (received prior antibiotic treatment for NTM vs did not receive prior treatment for NTM)

If the sample size is too small in one of the randomization stratification subgroups such that an adjusted analyses cannot be performed, unadjusted analyses will be used

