12.2 Secondary Efficacy Analyses

Secondary efficacy endpoints will be presented as collected. Missing data will not be imputed and no adjustment for ICEs will be performed. All secondary efficacy endpoints will be analyzed using the ITT analysis set. All secondary efficacy endpoints will be summarized using descriptive statistics at each scheduled time point by treatment group as described in [Section 6](#).

The Day 84 visit time point will be presented with data as collected. The Day 84/EOT visit timepoint will include subjects who end treatment on Day 84 as well as subjects who prematurely discontinue treatment.

Secondary endpoints, where appropriate, will be analyzed using an analysis of covariance (ANCOVA) model at each visit which will include the change from baseline as the dependent variable and randomized treatment group and stratification factor (prior antibiotic treatment for MABC NTM) as fixed factors and corresponding baseline score as a covariate. Model estimated least squares (LS) means, their SDs, and 95% CIs will be presented. The difference in LS means, SDs, 95% CIs, and a p-value testing the difference between treatment group LS means will be provided.

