12.2.9 Percentage of Subjects with a Decrease in Quantitative Mycobacterial Sputum

The ninth secondary efficacy endpoint is the percentage of subjects with a decrease in quantitative mycobacterial load from the sputum culture collected at the Day 84 visit and defined as a reduction in the semi-quantitative score (as defined in Table 10.3.2) as compared to baseline. The number and percentage of subjects with a reduction in the semi-quantitative score at the Day 84 visit will be presented for the ITT analysis set by treatment group. Exact 2-sided 95% CIs for the point estimate of the percentage of subjects with a decrease in each treatment group will be determined using the Clopper-Pearson method. The odds ratio (omadacycline relative to placebo) and p-value will be calculated using Cochran-Mantel-Haenszel test, stratified by prior antibiotic use. If the sample size is too small in one of the randomization stratification subgroups such that an adjusted analysis cannot be performed, an unadjusted analysis (chi-squared or Fisher's exact test) will be used.

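### The only PGI-S p-value uses neither baseline PGI-S nor the randomisation stratum, and the most-bothersome-symptom rule leaves some subjects unclassified

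*SAP*

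**What the plan says.** **PGI-S.** SAP 12.2.5 analyses PGI-S like PGI-C (SAP 12.2.4), except that "subject response will be grouped as subjects with responses of Not Present/Mild versus those with responses of Moderate/Severe". This is done at Days 28, 56, 84 and Day 84/EOT, with an exact confidence interval for the difference and a Fisher's exact p-value. Protocol 12.5.2.1 plans the same: "The PGI-S will also be categorized as mild/not present vs. moderate/severe", again with Fisher's test. The summary that does refer to baseline has counts and percentages only: "An additional analysis of the PGI-S will summarize change from baseline as improved, no change and worsened".

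**Comparable endpoints.** The binary culture endpoint in SAP 12.2.9 is stratified: "p-value will be calculated using Cochran-Mantel-Haenszel test, stratified by prior antibiotic use". QOL-B, SGRQ and PROMIS use the ANCOVA of SAP 12.2, with "stratification factor (prior antibiotic treatment for MABC NTM) as fixed factors and corresponding baseline score as a covariate". SAP 11.3 commits only to this: "some secondary efficacy analyses will include adjustments for randomization stratification factor".

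**Most bothersome symptoms.** SAP 12.3 calls a subject a responder if all three are absent or mild at Day 84, and a non-responder if at least one is worse than mild. SAP 10.1 and the form in protocol Appendix 4 let subjects name at most three, so fewer is allowed. Protocol 6.2 admits subjects with two symptoms and sets no severity threshold.

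**The concern.** A subject already in the Not Present/Mild category at Day 1 who does not change counts the same in the PGI-S comparison as one who moved there from Moderate/Severe. Appendix 1 schedules PGI-S at Day 1, so the information that separates them should be available, and prior antibiotic use is the randomisation factor. The one PGI-S comparison with a p-value uses neither. With 75 subjects, a baseline difference between arms passes straight into the result.

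The most-bothersome rule raises two questions: whether every subject can be classified, and whether the rate measures improvement or partly mild disease that was there at entry. A gap in the definition would have to be filled later by an unwritten rule. SAP 6 treats anything done after the blind is broken as post hoc.

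**Working it through.** **1. The plan's own figure.** The only power statement (SAP 5) is for the primary endpoint: about 80% for 15% versus 45% with 30 and 45 subjects.
- Pooled rate: (30×0.15 + 45×0.45)/75 = 0.33.
- Pooled SE: √(0.33×0.67×(1/30 + 1/45)) = 0.1108. Unpooled SE: √(0.15×0.85/30 + 0.45×0.55/45) = 0.0987.
- Power: Φ((0.30 − 1.96×0.1108)/0.0987) = 79.9%. Exact enumeration of the Mantel-Haenszel (MH) test gives 80.2%.

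The figure reproduces and is not in dispute. The documents give no rates or power for PGI-S.

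**2. PGI-S illustration.** All rates here are assumptions. Let q be the share Not Present/Mild at baseline (mild, for short) and k the probability that such a subject is still mild at Day 84, equal in both arms. Moderate/Severe subjects reach Not Present/Mild in 15% (placebo) and 45% (omadacycline), borrowed from the primary endpoint. The visit rates are then

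placebo = qk + (1−q)×0.15; omadacycline = qk + (1−q)×0.45.

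For q = 40% and k = 95% these are 0.38 + 0.09 = 47% and 0.38 + 0.27 = 65%. Fisher and unadjusted MH power are enumerated exactly. CMH stratified by baseline category is simulated (40,000 trials per cell). Power in %, for q = 20/40/60%:

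| k | Fisher | MH, unadjusted | CMH by baseline | Gain over MH (points) |
|---|---|---|---|---|
| 95% | 47.3/27.8/15.9 | 55.0/34.7/20.1 | 67.7/51.0/31.1 | 12.7/16.3/11.0 |
| 80% | 48.0/27.6/13.8 | 55.5/34.4/18.6 | 62.4/40.2/21.2 | 7.0/5.8/2.6 |
| 70% | 48.8/27.6/13.5 | 56.0/34.3/18.2 | 60.3/37.0/18.4 | 4.3/2.6/0.2 |
| 60% | 50.0/27.7/13.4 | 56.7/34.4/18.1 | 58.9/35.2/17.5 | 2.2/0.8/−0.6 |

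Moving from Fisher to unadjusted MH accounts for a further 4–8 points. Stratifying also by prior antibiotic use, with the collapsing rule given under the fix, gives results within about 1 point of the baseline-only column and usually slightly below it. Prior use was simulated with no effect on outcome, so the gain shown comes from baseline PGI-S alone. The rule's type I error is about 4.5–5.1%.

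**3. Cross-check with another model.** Correlated latent severity, 30% or 50% mild at baseline, a treatment shift of 0.7 SD: adjustment adds −2 to 0 points over unadjusted MH at a baseline/Day 84 correlation of 0.3, +1 to +3 at 0.5, and +7 to +9 at 0.7. Fisher's overall type I error is 3.2–3.6%, so ignoring baseline does not inflate it.

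**4. Chance imbalance.** By exact enumeration with 30 and 45 subjects, the arms differ in mild share by 10 points or more in 32/41/41% of trials at q = 20/40/60%. Ten extra points of mild subjects in one arm move the crude difference by 0.10×(k − rate among Moderate/Severe). At k = 95% that is 0.10×(0.95−0.45) = 5 to 0.10×(0.95−0.15) = 8 points; at k = 70% it is 2.5 to 5.5. In the latent model at correlation 0.7, when the imbalance favours omadacycline by at least 15 points (8–10% of trials), false positives in that direction are about 8% with Fisher and 2–3% with stratified CMH, against a nominal 2.5%.

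**5. Most bothersome symptoms: the definitions applied.**

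| Listed | At Day 84 | Class under SAP 12.3 |
|---|---|---|
| 3 | all absent or mild | responder |
| 3 | at least one worse than mild | non-responder |
| 1 or 2 | at least one worse than mild | non-responder |
| 1 or 2 | all absent or mild | neither |

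Read literally, a subject listing one or two symptoms can be a non-responder or unclassified, never a responder. A subject with three mild symptoms at baseline and the same three mild at Day 84 is a responder.

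**The case against.** The strongest reply is that nothing in SAP 12.2.5 is an error. It carries out the protocol's analysis. Its sister endpoint PGI-C uses the same unstratified Fisher test and CGI-I an unstratified Wilcoxon test, so the global impressions are handled alike. ANCOVA is reserved for change scores where appropriate, p-values are nominal, and adjustment was promised only for some secondary analyses. All of that stands. A reader might infer that the Fisher comparison is biased, or that the SAP breaks its own rule on covariates; the documents support neither.

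It is also fair that the gain depends on how strongly baseline predicts Day 84, which no document states, and that the largest gains come from the most favourable assumptions. Nor is any separate benefit from prior antibiotic use demonstrated; the case for including it is that it is the randomisation factor.

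On the most-bothersome rule, absent or mild is a legitimate target, no p-value is planned, and the baseline severity tables (SAP 10.1) and symptom shift tables (SAP 12.2.8) will show unchanged mild symptoms. That weakens the point about mild symptoms but does not close the classification gap. A reader might be tempted to say how far the placebo rate is inflated. That would need the share of subjects with only mild listed symptoms and a placebo rate for this rule. The 15% in SAP 5 belongs to a different endpoint.

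SAP 12.2.7 does not say whether the CGI-S Wilcoxon test uses the visit rating or the change from baseline described in protocol 12.5.2.1. That needs a clarifying sentence and is not part of this finding.

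**Conclusion.** Both parts hold, at minor to moderate weight. For PGI-S, the sole tested comparison leaves out a baseline value scheduled at Day 1 and the randomisation stratum. The consequence is lost precision and exposure to chance imbalance, not bias or an invalid test. The size rests on assumed transition rates: about 11–16 power points over unadjusted MH at 95% persistence, about 0–4 at 70%, about nil at 60% or below, plus about 4–8 for leaving Fisher's test.

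For the most-bothersome endpoint, the classification gap and the counting of unchanged mild symptoms follow from the wording alone and need no assumption. How many subjects are affected cannot be derived from the documents.

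**What to change.** **PGI-S.**
- Keep the split, the crude exact risk difference and the improved/no change/worsened summary.
- Take the p-value from a CMH test stratified by baseline PGI-S (Not Present/Mild versus Moderate/Severe) and prior antibiotic use. Name the Mantel-Haenszel stratified risk difference with 95% CI as the main estimate and the crude difference as descriptive, so that two differences do not compete.
- Fix the collapsing rule: if any of the four strata has no subjects in one arm, stratify by baseline category alone; if a baseline category has none in one arm, use Fisher's exact test.
- First reconcile two conflicts. Protocol 8.13.4 says "The PGI-S is a self-administered, single question assessed using a 7-point scale", while the split names four levels. Protocol 8.13 omits PGI-S from the Day 1 questionnaires, while Appendix 1 schedules it then.
- Record the change in SAP 14, which now reports none, before the blind is broken.

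**Most bothersome symptoms.**
- Define the responder as having all listed symptoms (one to three) absent or mild at Day 84. Report this in all subjects, and also in those with at least one listed symptom worse than mild at baseline.
- Reconcile when the list is taken: protocol 8.12 says Screening; Appendix 4 and SAP 10.1 say baseline.
- Protocol 12.5 leaves additional endpoints to the SAP, so no SAP 14 entry is needed.

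**Cost.** SAP wording and one extra PGI-S analysis, with little or no gain if baseline predicts Day 84 weakly. The four strata will sometimes collapse: with 20% mild at baseline, in about 10% of trials if half the subjects had prior antibiotics and about 41% if a fifth did. A subject without a baseline PGI-S cannot enter the stratified test. The restricted most-bothersome summary has fewer subjects, so it is added to the full one and does not replace it.

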12.2.6 Clinical Global Impression-Improvement (CGI-I)

The sixth secondary efficacy endpoint is the CGI-I response at the Day 28, 56, and 84 visit, and Day 84/EOT. The number and percentage of subjects with each response will be presented by treatment group. The p-value from a Wilcoxon rank sum test will be provided.

An additional analysis of the CGI-I will summarize change from baseline as improved, no change and worsened at the Day 28, 56 and 84 visit, and Day 84/EOT. The number and percentage of subjects in each change category will be provided.

12.2.7 Clinical Global Impression-Severity (CGI-S)

The seventh secondary efficacy endpoint is the CGI-S response at the Day 28, 56, and 84 visit, and Day 84/EOT. The CGI-S will be analyzed similarly to the CGI-I described in Section 12.2.6.

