For the PGI-C, the number and percentage of subjects with each response will be presented by visit and treatment group. The PGI-C will also be categorized as improved vs. no change/worse and the number and percentage of subjects in each category will be presented by visit and treatment group. Exact 2-sided 95% CIs using the Clopper-Pearson method for the percent improved and a p-value from Fisher's exact test will be provided.

Descriptive statistics for severity of illness from the CGI change from baseline for each visit will be presented by treatment group. Descriptive statistics of the global improvement and the efficacy index from the CGI will also be provided by treatment group for each visit. A p-value from the Wilcoxon rank sum test for each outcome will also be presented.

At each visit based on the NTM Symptom Assessment Questionnaire, the number and percentage of subjects with a new symptom (compared with baseline) with severity worse than mild and no new symptoms with a severity worse than mild will be summarized by treatment group. Shift tables from baseline for each symptom at each visit will also be provided.

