11.1 Efficacy Variables

The primary efficacy endpoints are:

- Clinical response (Definition 1) is defined as improvement at the Day 84 visit in severity of at least 50% of symptoms on the NTM Symptom Assessment Questionnaire present at baseline.

- Clinical response (Definition 2): is defined as improvement at the Day 84 visit in severity of at least 50% of symptoms on the NTM Symptom Assessment Questionnaire present at baseline and no deterioration in severity of any symptoms present at baseline.

Supportive analyses include analysis of clinical response (Definition 1 and Definition 2) at the Day 28 and Day 56 visits.

The secondary efficacy endpoints are:

- Change from baseline in Quality of Life - Bronchiectasis (QOL-B) domain scores at days 28, 56, 84, and Day 84/EOT
- Change from baseline in the St George's Respiratory Questionnaire (SGRQ) global and component scores at days 28, 56, 84, and Day 84/EOT
- Change from baseline in the Patient-reported Outcomes Measurement Information System (PROMIS) Fatigue 7a Short Form standardized score at days 28, 56, 84, and Day 84/EOT
- The Patient Global Impression – Change (PGI-C) response at days 28, 56, 84, and Day 84/EOT
- The Patient Global Impression – Severity (PGI-S) response at days 28, 56, 84, and Day 84/EOT
- The Clinical Global Impression – Improvement (CGI-I) response at days 28, 56, 84, and Day 84/EOT
- The Clinical Global Impression – Severity (CGI-S) response at days 28, 56, 84, and Day 84/EOT
- The percentage of subjects with a new symptom (defined as a symptom present post-baseline but absent at baseline) on the NTM Symptom Assessment Questionnaire with severity worse than mild at days 28, 56, 84, and Day 84/EOT
- The percentage of subjects with a decrease in quantitative MABC sputum culture from baseline to Day 84
- Time to growth in liquid medium only
- Time to first sputum culture negative for MABC

The additional efficacy endpoints are:

- Time to detection of MABC in growth media at baseline and the Day 28, 56, 84 and Day 84/EOT visits
- The percentage of subjects who convert from a positive MABC sputum culture at baseline to a sputum culture negative for MABC at any time post-baseline and at the Day 28, 56, 84 and Day 84/EOT visits
- In those subjects whose first negative culture (i.e., convert from a positive MABC sputum culture at baseline to a negative MABC sputum culture) is on the Day 28, 56, 84 and Day

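### The SAP moves the CGI-S p-value from change from baseline to the visit score and omits the CGI efficacy index, yet Section 14 declares no changes from the protocol (minor)

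*SAP*

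**What the plan says.** **Protocol 12.5.2.1.** On CGI-S: "Descriptive statistics for severity of illness from the CGI change from baseline for each visit will be presented by treatment group". On the other CGI outcomes: "Descriptive statistics of the global improvement and the efficacy index from the CGI will also be provided by treatment group for each visit". The paragraph ends: "A p-value from the Wilcoxon rank sum test for each outcome will also be presented". Read together, these give three outcomes, each with a Wilcoxon test: CGI-S change, global improvement and the efficacy index.

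**SAP 11.1.** The CGI-S endpoint is listed as "The Clinical Global Impression – Severity (CGI-S) response at days 28, 56, 84, and Day 84/EOT". The same list words other endpoints as changes, for example "Change from baseline in Quality of Life - Bronchiectasis (QOL-B) domain scores".

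**SAP 12.2.7 and 12.2.6.** For CGI-S: "The CGI-S will be analyzed similarly to the CGI-I described in Section 12.2.6". In 12.2.6, the sentence after the counts of each response is "The p-value from a Wilcoxon rank sum test will be provided". A separate paragraph then sorts change from baseline into improved, no change and worsened, and ends: "The number and percentage of subjects in each change category will be provided". That paragraph has no test.

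**SAP 14.** It states that nothing departs from the protocol's analyses. The efficacy index does not appear anywhere in the SAP text.

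**Day 1 collection.** The Schedule of Assessments (Protocol Appendix 1) marks both CGI-S and PGI-S at Day 1. Protocol 8.13 names only QOL-B, SGRQ and PROMIS Fatigue as patient-reported measures collected on Day 1.

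**The concern.** The borrowed method does not carry the same meaning from one scale to the other. Protocol 8.13.7 describes CGI-I as a rating of improvement relative to baseline, so a test on its visit score is already a test of change. Protocol 8.13.6 describes CGI-S as severity over the past seven days. Applying the CGI-I test to CGI-S therefore removes the baseline reference that the protocol put there.

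Two things are at stake. The first is traceability. The two documents lead to different CGI-S p-values, and a reader who relies on Section 14 would not know that the test had moved or that the efficacy index had gone. SAP Section 1 commits only to recording departures from the SAP in the study report, so a change made between protocol and SAP can miss both records. The second is precision: with 45 and 30 subjects, a test that ignores the Day 1 score gives up information the schedule says is collected.

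**Working it through.** **1. The texts side by side**

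| Item | Protocol 12.5.2.1 | SAP |
|---|---|---|
| CGI-S variable that carries the p-value | change from baseline | response at the visit (12.2.7 via 12.2.6) |
| CGI-S change from baseline | summarised and tested | three-category counts, no test |
| CGI efficacy index | summarised and tested | not mentioned |
| Declared in Section 14 | – | no changes |

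Both differences contradict Section 14.

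**2. Does the SAP's ANCOVA cover CGI-S?** SAP 12.2 offers a model with baseline score and stratum for secondary endpoints where appropriate. Only 12.2.1 to 12.2.3 (QOL-B, SGRQ, PROMIS) invoke it. Section 12.2.7 points to 12.2.6 instead.

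**3. Which test is more precise?** The documents give no power figure for CGI-S. The stated 80% is for the primary endpoint; it reproduces at 79.9% (15% vs 45%, 30 vs 45 subjects, pooled normal approximation) and does not bear on this point.

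Inputs: 45 and 30 subjects (SAP Section 5) and two-sided 0.05. Assumed: a treatment shift of 0.6 SD, equal SD at both times, continuous scores, complete data, and a baseline-to-visit correlation rho of 0.2 to 0.7.

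Variance of the treatment contrast relative to the visit score:
- visit score: 1
- change score: 2(1 − rho)
- baseline-adjusted (ANCOVA): 1 − rho²

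Change beats the visit score only if 2(1 − rho) < 1, that is rho > 0.5. ANCOVA is never worse than the visit score, since 1 − rho² ≤ 1. It is never worse than change, since 1 − rho² = (1 − rho)(1 + rho) ≤ 2(1 − rho).

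SE for the visit score = sqrt(1/45 + 1/30) = 0.236, so 0.6/SE = 2.546. Power = Φ(2.546/√v − 1.96), where v is the relative variance.

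| rho | v: change | v: ANCOVA | Power: visit | Power: change | Power: ANCOVA |
|---|---|---|---|---|---|
| 0.2 | 1.60 | 0.96 | 72% | 52% | 74% |
| 0.3 | 1.40 | 0.91 | 72% | 58% | 76% |
| 0.5 | 1.00 | 0.75 | 72% | 72% | 84% |
| 0.7 | 0.60 | 0.51 | 72% | 91% | 95% |

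**4. Check on ordinal scores.** The simulation used 3,000 trials per scenario, the same shift, and five assumed mixes over 4 or 7 levels (Protocol 8.13.6 gives no number of CGI-S levels). Visit-score Wilcoxon minus change-score Wilcoxon was +14 to +24 points of power at rho 0.2–0.3, +3 to +9 at 0.5, −7 to +2 at 0.6, and −5 to −15 at 0.7. Adding baseline to the same linear model gained about 1–3 points at 0.2–0.3 and 8–21 at 0.5–0.7. With no effect, the visit Wilcoxon, change Wilcoxon and ANCOVA rejected in 4.2–5.6%, 4.1–5.6% and 4.3–5.7% of trials, so all three hold their level.

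**The case against.** **The wording leaves room.** The SAP says only that CGI-S is analysed similarly, the inherited text includes a change-from-baseline summary, and the ANCOVA sentence does not exclude CGI-S. This stands in part: the SAP has not dropped CGI-S change; only its test has moved. But 12.2.7 names the response as the endpoint, the p-value sits with the response counts, and no reading of the text restores the efficacy index.

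**The efficacy index may never have been collected.** This stands. It is not a listed endpoint, Protocol 8.13.6 and 8.13.7 do not define it, and the schedule has no row for it. A reader might infer that it can simply be added from existing data; the documents do not show that.

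**The SAP's test may be the better one.** This also stands. Below a correlation of about 0.5 the visit score is stronger, so merely going back to the change-score test could lose up to 24 points in the simulations. At low correlation the adjusted test gains only a point or two over the visit score.

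**These p-values decide nothing.** SAP Section 6 says they test no pre-specified hypotheses, and CGI-S is the seventh secondary endpoint. In the simulations the visit and change tests fell on opposite sides of 0.05 in 30–36% of trials with a 0.6 SD effect. A reader might infer that the study's conclusion is at risk. It is not: the rate rests on assumed inputs, and no decision hangs on that threshold.

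**Conclusion.** The CGI-S p-value and the efficacy index both differ from Protocol 12.5.2.1, and Section 14 is wrong as written. That is certain from the text. The loss of precision is real in principle, but its size is unknown: negligible at low correlation and large at 0.5 to 0.7, a range assumed here. Observed-data analysis with dropouts would lower all the powers shown.

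Two stronger readings are not supported. One is that the SAP's CGI-S test is biased or invalid; under randomisation it is neither. The other is that PGI-S shows the same departure. It does not: Protocol 12.5.2.1 itself specifies Fisher's test on not present or mild against moderate or severe, and SAP 12.2.5 follows it. In the simulations 16–24 points of the PGI-S power gap came from dichotomising, not from leaving out Day 1.

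The mismatch between Protocol 8.13 and Appendix 1 on Day 1 PGI-S is a separate inconsistency. It matters because the PGI-S change summary in SAP 12.2.5 needs that score. Severity: minor.

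**What to change.** 1. **CGI-S.** Keep the planned tables. At each visit, add a comparison adjusted for Day 1 CGI-S and prior-antibiotic stratum, using the SAP 12.2 ANCOVA or a rank ANCOVA. List the departure from Protocol 12.5.2.1 in Section 14.
2. **Efficacy index.** State in Section 14 that it will not be analysed, or analyse it only if it was collected.
3. **Day 1 PGI-S.** Reconcile Protocol 8.13 with the Schedule of Assessments.
4. **Timing.** The SAP's audit page shows version 5.0 signed on 2024-09-23. If the blind is already broken, label the added model post hoc, as SAP Section 6 requires, and record the CGI-S and efficacy-index departures in the study report.

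A baseline-adjusted PGI-S model is an optional supportive addition, not a correction.

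The cost is a few lines of text and a few outputs from a model the SAP already specifies. No new CGI-S data are needed if Day 1 was collected as scheduled. The downsides are that subjects without a Day 1 score drop out of the adjusted comparison, and ANCOVA treats an ordinal score as numeric. Rank ANCOVA avoids the second, at a cost of at most 2.6 points of power in the simulations at a 0.6 SD shift.
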